The endpoint for Aim 1 for the intervention arm is the successful completion of the follow-up period, including food and nutrition security status, total fruits and vegetables selected per visit, total energy intake, intake of key food groups, and time to obtain food from food pantry per visit.

The endpoint for Aim 2 is the completion of data analysis.

Study Population

The study population for Aim 1 is a sample of low-income adults aged ≥ 18 years..

Accrual Ceiling

We require a total sample size of 193 participants per condition for Aim 1 (total n=386).

Aim 2 will not involve participant enrollment.

Phase

Not applicable.

Description of Sites/Facilities Enrolling Participants

We propose to recruit participants from food pantry clients at food pantry sites within the Met Council Kosher Food Pantry Network, a network that contains 65 pantry partners and over 200 community partners in NYC. Met Council procures and distributes kosher food to their network of kosher food pantries and provides ongoing support with reporting, pantry set up and maintenance, advocacy, and programming. The Network primarily serves immigrants, seniors living on fixed incomes, the un- and underemployed and anyone else in need in immigrant-dense neighborhoods.

Study Duration

The study will last 18 months, but data collection will specifically occur in 2 time periods, including months 4-6 and 10-12 in Year 1 of the study.

Participant Duration

The total participant duration will be approximately 30-50 minutes to complete the survey and record food selections for both data collection periods.

Schedule of Activities (SoA)

During the baseline data collection period, all participants will complete a survey about their food and nutrition security, diet behaviors, and frequency of food pantry visits. To finish, the Research Assistant will record their food selections from the current food pantry visit.

During the follow-up data collection period, all participants will complete a survey about their food and nutrition security, diet behaviors, and frequency of food pantry visits. Participants in the control arm will record their food selections from their most recent food pantry visit and send them to the study team.

End of Study Definition

The end of the study is when we have disseminated our results.

1 – Statement of Compliance

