4.1 Overall Design

This research study includes two aims, though only Aim 1 involves human subjects. The duration of the study is 18 months.

In Aim 1, study team members will recruit low-income adults aged ≥ 18 years. Participants will be recruited from a food pantry that is not scheduled to transition to online ordering (control) and a food pantry that is scheduled to transition to online ordering after the baseline data collection period (intervention). Participants in both arms will complete an in-person survey. Potential participants who are not able to take the survey in-person, will be offered the option to take the survey online. To assess potential changes in fruit and vegetable intake, we will administer the Behavioral Risk Factor Surveillance System (BRFSS) 6-item brief dietary assessment tool (questions 9-14 in the survey attached in Research Navigator). A Research Assistant will record the food items they received in the relevant visit to the pantry. After the transition to online ordering at the intervention food pantry, participants will again complete the survey over the phone. The survey will be administered by a member of the study team using the Follow-Up Survey Guide. Participants in the control arm will record their food selections and send them to the study team during the phone call. Food selections for participants in the intervention arm will be accessible through the online ordering platform. The study team will then analyze the baseline and follow-up data for differences in outcomes between study conditions.

In Aim 2, we will test for potential interaction effects at the individual-level by adding an interaction term for age group (18-61 vs. ≥ 62 years).

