Prior to the follow-up period, the study team will provide the food pantry with a flyer and post-card-sized handouts to remind participants of the upcoming follow-up surveys.

Aim 2 will not involve any participant recruitment.

6 - Study Procedures

6.1 Aim 1

Data collection in the baseline period will occur during the two to four month period prior to the intervention month (months t-2 to t-4), and data collection in the follow-up period will occur during the two-to-four-month period after the transition to digital ordering (months t+2 to t+4). The months immediately preceding (t-1) and following (t+1) the intervention month will be omitted to account for potential uncertainty in the implementation of online ordering and to allow for sufficient time for food pantry clients to return to their food pantry, respectively.

For the baseline period/visit (in person), consent will take place in person at the food pantry and data collection will take place in person at the food pantry, with the option to take the survey online offered on a case-by-case basis. The following will occur for both arms:

- Participants will be asked to complete a survey about their food and nutrition security, diet behaviors, and frequency of food pantry visits. The survey will take about 10 minutes to complete. Survey responses will be collected using Qualtrics.
- We will administer the Behavioral Risk Factor Surveillance System (BRFSS) 6-item brief dietary assessment tool to participants in both arms to assess potential changes in fruit and vegetable intake (questions 9-14 in the survey attached in Research Navigator).
- Participants will be given a card with an appointment time of their choosing that falls within the follow-up period, which will also include the phone number for an IRB-approved NYULH study personnel that they can reach if they need to re-schedule.
- The food pantry items selected by participants will be documented in-person by the Research Assistant. It will take approximately 5 minutes for the Research Assistant to record the participants' food selections.

For the follow-up period/visit (virtual/phone):

- **Intervention Arm**
 - We will send follow-up reminders to participants via email and/or text, based on their preference.

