 - Participants will be asked to complete a survey by phone about their food and nutrition security, diet behaviors, and frequency of food pantry visits. The survey will take approximately 20-25 minutes to complete. The survey will be administered by a member of the study team using the Follow-Up Survey Guide.
 - Data on participants' food selections will be gathered from the online ordering system. This data will be provided to the study team by Met Council. Participants will not need to wait for the Research Assistant to record their selections.

- **Control Arm**

- We will send follow-up reminders to participants via email and/or text, based on their preference.
- Participants will be asked to complete a survey by phone about their food and nutrition security, diet behaviors, and frequency of food pantry visits. The survey will take approximately 20-25 minutes to complete. The survey will be administered by a member of the study team using the Follow-Up Survey Guide.
- Since the follow-up data collection occurs virtually and the study team will not be on site at the food pantry to record food selections, we will instruct participants to take a photo of their selections at their next food pantry visit and email or text the photo to the research team, using the information on the appointment card. It will take approximately 5 minutes for participants to record their food selections and send them to the study team. If participants do not remember to take the photo, we will assess their recall of their selections during the follow-up conversation.

6.2 Aim 2

We will test for potential interaction effects at the individual-level by adding an interaction term for age group (18-61 vs. ≥ 62 years). We will use the data collected for Aim 1 to complete these analyses. No additional data will be collected for Aim 2.

7 - Participant Discontinuation/Withdrawal

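### The visit that supplies follow-up food selections is worded inconsistently for the control arm and undefined for the intervention arm, and capture mode also differs by arm

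*Combined protocol and SAP*

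**What the plan says.** Three places describe how control-arm food selections are obtained at follow-up.

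- Synopsis, Schedule of Activities: "Participants in the control arm will record their food selections from their most recent food pantry visit and send them to the study team".
- Section 4.1, Overall Design: "Participants in the control arm will record their food selections and send them to the study team during the phone call".
- Section 6.1, Aim 1, control arm: "we will instruct participants to take a photo of their selections at their next food pantry visit", to be emailed or texted using the contact details on the appointment card. The fallback is: "If participants do not remember to take the photo, we will assess their recall of their selections during the follow-up conversation".

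For the intervention arm, Section 6.1 says "Data on participants' food selections will be gathered from the online ordering system", supplied by the pantry network. It does not say which order, how many orders, or orders from which dates.

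Section 6.1 places follow-up data collection in months t+2 to t+4 and leaves out months t-1 and t+1. At baseline, a Research Assistant documents the selections in person in both arms.

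**The concern.** A per-visit outcome needs a defined visit. Here the control arm has two descriptions of it that need not agree, and the intervention arm has none. Staff working from different sections could collect different visits. An analyst given the order file would have to choose between one order, several orders or an average after the data are in hand.

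The way selections are captured also separates completely by arm at follow-up: system records in one arm, photographs or memory in the other. Any difference in timing or measurement is then confounded with the transition to online ordering. The outcome at stake is the change in cup-equivalents of fruits and vegetables selected per visit, listed first in Section 8.4.3 and part of the second hypothesis in Section 8.1.

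**Working it through.** The plan gives no figure on this point. Its sample size calculation (Section 8.2) concerns the food security score and does not bear on food selections. The check is a comparison of the text, followed by the algebra of the bias.

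**1. Which visit, when and how, for controls**

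- Synopsis: the visit is the most recent one; the time and means of sending are not given.
- Section 4.1: no visit is named; selections are sent during the call.
- Section 6.1: the visit is the next one; a photo is sent by email or text. When the instruction is given is not stated, so *next* has no fixed starting point.
- Section 6.1, fallback: recall during the call; no visit is named.

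Only the Synopsis and Section 6.1 name a visit. Section 4.1 differs from Section 6.1 on when and how the selections are sent.

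**2. When *next* and *most recent* agree**

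- If the photo instruction goes out with the pre-call reminder and the participant then makes one visit before the call, the next visit is also the most recent one at the time of the call.
- If the participant makes two or more visits between the reminder and the call, they are different visits.
- If the instruction were given during the call, the next visit would come after it.

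The text does not say which case applies.

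**3. The window**

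The synopsis timeline puts the transition in month 8, so t+2 to t+4 is months 8+2=10 to 8+4=12, matching its follow-up months. That window dates the data collection. No sentence says that the visit being photographed or recalled, or the order extracted, must itself fall inside it.

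**4. What the comparison between arms estimates**

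Let *b* be the average error in recorded selections under a given method, including any error from describing the wrong visit. Let *p* be the share of controls whose selections are recalled.

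- Baseline: the method is the same in both arms, so its error cancels if it is equal in the two arms (an assumption).
- Follow-up, intervention: b_order.
- Follow-up, control: (1 − p) × b_photo + p × b_recall.
- Bias in the difference in change = b_order − [(1 − p) × b_photo + p × b_recall].

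Subtracting baseline does not remove this term, because the method changes after baseline and changes differently by arm. Adjustment for unbalanced respondent characteristics (Section 8.4) does not remove it either. The documents give no value for p or for any *b*, so neither the size nor the sign can be calculated.

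**5. What a sensitivity analysis can do**

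Dropping recalled selections sets p = 0 and leaves b_order − b_photo. The recall component goes; the difference between order record and photo stays, because that difference coincides with arm. Sections 8.4 to 8.4.8 contain no such analysis and no capture-mode variable.

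**The case against.** The best defence is that the procedures hang together when read in context. The photo instruction sits under the follow-up heading of Section 6.1, in a list that opens with reminders. Recall during the call replaces a forgotten photo, which implies that the photo was meant to come first. On that reading, the next visit after the reminder is usually the most recent visit at the call. The Follow-Up Survey Guide, which is not among the documents, may also name the visit to be recalled. Much of this stands: the intended sequence is probably sensible. It does not supply a stated rule for controls, and it does nothing for the intervention arm, where no order is identified.

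A reader might infer three stronger things that the documents do not support.

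- *Three conflicting rules for which visit.* Only two places name a visit, and those two can coincide.
- *Control photos taken before the transition.* Section 6.1 says of the baseline visit: "Participants will be given a card with an appointment time of their choosing that falls within the follow-up period". The photo is sent using details on that card, so one might suppose that the instruction is also given at baseline. No section says so. The card supplies contact details, and a photo from that time would fall outside the stated follow-up period.
- *A definite percentage bias in favour of online ordering.* This would need a share of controls using recall and a rate of omitted items, and the plan gives neither. Recall can add items as well as lose them, so the direction is not known.

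**Conclusion.** The concern holds as a gap in definition and a difference in measurement between arms. The control-arm index visit is inconsistently worded, the intervention-arm index order is undefined, and capture mode at follow-up separates by arm. For fruit and vegetable cup-equivalents selected per visit, timing and measurement are therefore confounded with online ordering.

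Size and direction are unknown. The conclusion rests on the protocol text alone; the survey guide could narrow the ambiguity about recall. The primary outcome comes from the six-item food security survey (Section 8.4.2) and is not touched. This is an inexpensive improvement to one secondary outcome and does not threaten the main result.

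**What to change.** Reconcile the Synopsis, Section 4.1 and Section 6.1 to one rule for both arms: the index visit is the last completed pantry visit (or order) within t+2 to t+4 and before the follow-up call.

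- **Intervention arm:** use the order record for that visit.
- **Control arm:** give the photo instruction in the reminder already planned, sent early enough to precede a pantry visit in the window. A visit already over when the reminder arrives cannot be photographed, so a late reminder would push more participants to recall.
- **No photo:** recall refers to that same index visit, and the survey guide says so.
- **No visit in the window:** state the handling, the same in both arms.
- **Analysis:** record capture mode (order record, photo, recall) for each participant and repeat the analysis without recalled selections.

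The cost is wording in three places, the timing and text of the reminder, one extra variable and one extra analysis. That analysis has a smaller control sample, made up of those who remembered the photo, so it should support the main analysis and not replace it. It cannot separate order record from photo, and the report should say so.

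### At follow-up, food selections come from order records in one arm and from photo or recall in the other, so recording method cannot be separated from online ordering for the fruit-and-vegetable selection outcome

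*Combined protocol and SAP*

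**What the plan says.** **Baseline, both arms.** Section 6.1 states: "The food pantry items selected by participants will be documented in-person by the Research Assistant". Section 4.1 describes the same step in terms of what was received: "A Research Assistant will record the food items they received in the relevant visit to the pantry".

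**Follow-up, intervention arm.** Section 6.1 says that data on "food selections will be gathered from the online ordering system", supplied by the pantry network. Section 4.1 agrees: "Food selections for participants in the intervention arm will be accessible through the online ordering platform".

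**Follow-up, control arm.** Because follow-up is virtual and no staff are on site, section 6.1 tells participants to "take a photo of their selections at their next food pantry visit" and send it in. The fallback is: "If participants do not remember to take the photo, we will assess their recall of their selections during the follow-up conversation". The Synopsis (Schedule of Activities) refers to the most recent visit, not the next one.

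**Survey outcomes.** These are collected the same way in both arms. Section 6.1 gives both arms the same text: "Participants will be asked to complete a survey by phone about their food and nutrition security, diet behaviors, and frequency of food pantry visits". Section 4.1 confirms that "participants will again complete the survey over the phone".

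**Use of the selection data.** Section 8.4.3 lists change in cup-equivalents of fruit and vegetables selected per visit as the first secondary outcome and reuses fruit and vegetable selections for Aim 2. Section 8.1 makes greater selection part of the second hypothesis. Section 8.4 regresses each outcome on condition and adjusts, if needed, only for respondent characteristics that are out of balance.

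**The concern.** Every intervention participant has one follow-up source and every control participant another. A difference between arms in the change in selections, or the lack of one, could come from how selections were recorded and not from online ordering.

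An order record is itemised by the system. A photo can hide or omit items, and recall can omit or add them. What was ordered may also differ from what was handed over, which matters if the outcome means items received, as the section 4.1 wording for baseline suggests.

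The stake is one secondary outcome, but a central one. Section 2.3.2 presents the study as evidence on how online ordering affects clients' food selection, for pantries deciding whether to transition. The survey measure of fruit and vegetable intake is comparable across arms, but it measures intake and cannot stand in for selection.

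**Working it through.** **1. Sources side by side (sections 4.1 and 6.1).**

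| | Baseline | Follow-up |
|---|---|---|
| Intervention | Research Assistant | Order record |
| Control | Research Assistant | Photo, else recall |

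**2. What the contrast estimates.** Let d be the true effect of online ordering and t the common change over time. Let s(RA), s(order) and s(photo/recall) be the average recording error of each source.

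- Mean change, intervention: t + d + s(order) − s(RA)
- Mean change, control: t + s(photo/recall) − s(RA)
- Difference in change: d + [s(order) − s(photo/recall)]

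The shared baseline term cancels, but the bracket does not.

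**3. Can a covariate remove it?** The design with intercept, arm, period and arm-by-period has rank 4. Adding one indicator for order record and one for photo/recall leaves the rank at 4. The contrast between order record and photo/recall is fully aliased with the intervention effect, so no regression on these data can separate them.

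**4. Aim 2.** The bracket drops out of the age interaction only if it is the same at 18–61 and at 62 or older. Nothing in the documents establishes that.

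**5. Other outcomes.** Food security, fruit and vegetable intake (the brief dietary tool, survey questions 9–14) and individual visit frequency come from the same phone survey in both arms. No arm difference in source is documented for pantry-level visits. The documents do not state the source for time to obtain food, so no claim is made about it.

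**6. Size.** The plan gives no mean, SD, recording error, baseline-to-follow-up correlation or power for selections, so there is no figure to reproduce. Section 8.2's 155 per arm is for the food security score and is borrowed here only as a sample size. What follows is illustration, not an estimate.

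*Direction.* Let a and c be the ratios of recorded to true for order records and for photo/recall. The false gap is (a − c) × mean. If both are assumed to lie between 0.9 and 1.1, it runs from −20% to +20% of the mean, centred on zero.

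*False rejection with no true effect.* Let b be the gap in SDs of the analysed variable, with 155 per arm and an assumed two-sided 5% test. SE = sqrt(2/155) = 0.114 SD, and the rejection probability is Φ(b/SE − 1.96) + Φ(−b/SE − 1.96).

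| b (SD) | 0 | 0.1 | 0.2 | 0.3 | 0.5 |
|---|---|---|---|---|---|
| Rejects | 5% | 14% | 42% | 75% | 99% |

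*Dependence on the model.* Section 8.4 does not fix a change-score or a baseline-adjusted model. Assume a net gap of 10% of the mean, SD/mean of 0.5 to 1.0, correlation r of 0 to 0.7, and equal SDs.

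- Change score: SE = SD × sqrt(4(1 − r)/155), which is 0.161 SD at r = 0 and 0.088 SD at r = 0.7. The shift is 0.10/0.161 = 0.62 to 0.20/0.088 = 2.27 standard errors, and rejection is about 10% to 62%.
- Baseline-adjusted: SE = SD × sqrt(2(1 − r²)/155), which is 0.114 to 0.081 SD. Rejection is about 14% to 69%.

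These ranges follow from the assumed inputs and bound nothing. A larger sample would not shrink the gap; it would only make rejection more likely for a given gap.

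**The case against.** **The choice is explained.** Section 6.1 gives the reason: follow-up is virtual and no staff are on site. That explains why a Research Assistant does not record selections again. It does not explain why the arms need different methods, since intervention participants also get reminders and a phone call.

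**Order records may be the better data.** The outcome is items selected, and an order record captures that directly. This stands for the intervention arm and is a reason to keep the records. It does nothing about photo and recall error in the control arm.

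**Methods are tested in advance.** Section 9.8 plans testing of the survey tool and dietary assessment methods before enrolment. That may improve each method, but it does not make the follow-up method common to both arms.

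**Site is confounded with arm anyway.** Sections 4.1 and 5.5 describe one pantry per arm, and no change in recording removes that. This stands as a limit on any fix. Recording method is a separate problem and cheaper to reduce.

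**Stronger readings that a reader might infer.** One is that the design favours online ordering because control participants will forget items. The documents do not support a direction: recall can also over-report, and orders can differ from what is received. Another is that the next-visit and most-recent-visit wordings contradict each other. They need not, because the visit photographed as the next one may be the most recent by the time of the call. The wording needs clarifying, no more.

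**Conclusion.** The concern holds for one outcome: change in fruit and vegetable cup-equivalents selected per visit, including its reuse in Aim 2. For that outcome, recording method is fully aliased with arm, and nothing in the planned analysis can separate the two. This conclusion rests on the documented sources alone and needs no numerical assumption.

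The size and direction of the bias cannot be found from the documents. The rejection rates shown are illustrative and depend on assumed recording error, SD, correlation, test level and model.

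A reader might infer that the trial's main result, or all its secondary results, are compromised. The documents do not support that. The primary outcome and the other survey outcomes use the same phone procedure in both arms. The change should be made because a named secondary outcome cannot be interpreted as planned and the remedy is cheap.

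**What to change.** **Collection (section 6.1).** Ask intervention participants for the same photo, or the same recall prompt on the follow-up call they already receive, for the same index visit. Keep obtaining order records. Record for each participant whether a photo or recall was used. Clarify in section 6.1 and the Synopsis which visit is the index visit, and match the order record to it.

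**Analysis (section 8.4.3).**
- Report the between-arm contrast on the common photo/recall measure alongside the contrast that uses order records.
- Within the intervention arm, compare photo/recall with order records, noting that this mixes reporting error with differences between ordered and received items.
- Label any photo-only analysis as selected on post-baseline behaviour (remembering to take and send the photo), which may differ by arm.

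**Interpretation.** State that a difference seen only with order records may reflect the recording method. Do not make agreement of the two contrasts the test for attribution. Both share the control-arm data, itemised ordering may aid recall in the intervention arm, and site remains confounded with arm.

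**Cost.** By the protocol's own estimate for control participants, about 5 minutes each: 193 × 5 = 965 minutes, or about 16 hours of participant time. Add some staff time for prompts and photo coding, some missing photos, and a minor amendment. Texted photos may bring carrier fees (section 10.2) and extend the unencrypted-texting risk already disclosed in section 2.3.1; email or recall on the call avoids texting. Section 9.6 already plans to link selection data by study ID. No extra visit is needed.

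If follow-up is already complete, which the documents do not say, the limit on attribution should still be stated when the outcome is reported.
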